### **13.2 Protocol Deviations**

Before closing the database, data listings will be reviewed to identify any significant deviations and determine whether the data should be excluded from any analysis populations.

Major protocol deviations include patients who:

- Entered the study even though they did not satisfy the entry criteria.
- Met the criteria for withdrawal from the study but were not withdrawn.
- Received the wrong treatment or incorrect dose.
- Received an excluded concomitant therapy.
- Received investigational product(s) past the expiration date.
- Had their treatment assignment unblinded.
- Visits outside of assessment windows

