6.2 YF476 administration

- Each study patient will self-administer the YF476 or placebo.
- The study medication will be dispensed into bottles: 46 capsules of 25 mg YF476 or placebo per bottle. 1 bottle will be dispensed to participants at the baseline visit (Visit 2) and at the Week 6 visit.
- Study medication should be taken once daily, in the morning, with breakfast. But, if a patient takes the study medication without food, or at a different time of the day, it will not be recorded as a protocol deviation. Missed doses will be recorded as protocol deviations.

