## 9 Analysis Populations

The following populations will be identified:

Screened Population: All patients screened for the study.

Safety Population: All patients who are randomised and received at least one dose of the study drug. In this population, treatment will be assigned based upon the treatment patients actually receive regardless of the treatment to which they were randomized.

Intent-to-Treat (ITT) Population: All randomised patients who receive at least one dose of study medication and had at least one post-baseline assessment. In this population, treatment will be assigned based upon the treatment to which subjects were randomised regardless of which treatment they actually received.

Per Protocol (PP) Population: All randomized patients who receive at least one dose of study medication and had at least one post-baseline assessment and did not have any major protocol deviations.

In all populations (apart from ITT) treatment will be assigned based upon the treatment patients actually receive regardless of the treatment to which they were randomised.

The primary endpoint will be analysed using the ITT population.

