### **13.4 Treatment Compliance**

The percentage treatment compliance at each visit will be listed and summarised.

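### As the SAP is written, a late follow-up visit removes the whole patient, including valid Week 6 and Week 12 data, from the per-protocol set

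*SAP*

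**What the plan says.** SAP 9 defines the PP population as randomised patients who took at least one dose, "had at least one post-baseline assessment and did not have any major protocol deviations". SAP 13.2 lists what counts as major, and one item is "Visits outside of assessment windows", with no limit to particular visits. The window is ±4 days for clinic visits in general (SAP 12.3, protocol 8.6). SAP 12.3 tells the analyst to disregard windows for the safety and ITT populations; PP is not mentioned.

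The primary endpoint runs from Visit 2 to Week 12 (SAP 4.2.1). Follow-up comes four weeks after study drug stops (protocol 8.5).

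On exposure, the closest item in SAP 13.2 is "Received the wrong treatment or incorrect dose". Protocol 6.2 says "Missed doses will be recorded as protocol deviations", without grading them. SAP 13.4 says "The percentage treatment compliance at each visit will be listed and summarised", without tying the result to PP membership.

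SAP 15 uses PP for summaries of serum gastrin and CgA, produced only where PP differs from ITT. SAP 3 places the other efficacy data, and so Ki67, in a separate report. SAP 4.3 plans no formal testing, and SAP 9 assigns the primary endpoint to ITT. Protocol 6.7 and 13.1 promise a per-protocol analysis but do not define its set.

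**The concern.** A PP set should keep patients whose treatment and measurements followed the plan closely enough to show what the drug does when taken as intended. A window deviation matters for the measurement taken at that visit. Here it acts on the patient: one late visit of any kind removes every measurement, including those taken on time. Follow-up shows this most clearly. By then the Week 6 and Week 12 samples and the Week 12 biopsy have been taken, and lateness afterwards cannot alter them.

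At stake is who appears in the PP summaries of gastrin and CgA, which are secondary endpoints. SAP 9 is also the only definition of a PP set in either document, so a separate Ki67 report could adopt it by default. With 20 planned completers, each patient is 5% of the sample.

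A second, softer gap concerns dosing. Capsule counts and diary cards are collected (protocol 6.7), but no written criterion says how much missed drug takes a patient out of PP.

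**Working it through.** **1. Reach of the rule.** SAP 13.2 (any out-of-window visit is major), SAP 9 (any major deviation removes the patient from PP) and SAP 12.3 (windows waived for safety and ITT only) together mean that an out-of-window Week 6, Week 12 or follow-up visit each removes the patient from PP.

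**2. Patients lost.** The documents give no lateness rate. Assume each of these three visits is independently out of window with probability p, and start from 20 patients.

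- Share removed under the written rule: 1 − (1 − p)³
- Share removed if only Week 12 counts: p
- Patients removed by follow-up alone: 20 × (1 − p)² × p

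| p | Removed, written rule | Left of 20 | Left if only Week 12 counts | Lost through follow-up alone |
|---|---|---|---|---|
| 5% | 1 − 0.95³ = 14.3% | 17.1 | 19.0 | 20 × 0.9025 × 0.05 = 0.9 |
| 10% | 1 − 0.90³ = 27.1% | 14.6 | 18.0 | 20 × 0.81 × 0.10 = 1.6 |
| 20% | 1 − 0.80³ = 48.8% | 10.2 | 16.0 | 20 × 0.64 × 0.20 = 2.6 |

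Follow-up is thus a minority of the total loss. The rest comes from Week 6 and from Week 12 itself.

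**3. Power, only if a Ki67 PP comparison reuses this set.** Inputs from SAP 8.1 and protocol 13.7: two-sided 0.05, 10 per arm, difference 0.25, SD 0.16. Power is that of the two-sample t-test (noncentral t, df = 2n − 2), with noncentrality 0.25 / (0.16 × √(2/n)).

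- n = 10: noncentrality 3.494, power 91.0%. The plan's table gives 91%, so it reproduces. Its headline cell (0.30, SD 0.16) also reproduces: 97.7% against 98%.
- n = 9 (18.0 of 20, p = 10%, only Week 12 counts): noncentrality 3.315, power 87.5%.
- n = 7 (14.6 of 20, p = 10%, written rule, rounded down): noncentrality 2.923, power 76.5%.

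The relevant contrast at 10% lateness is 77% against about 87%. Comparing 77% with 91% would charge the rule with patients whose Week 12 visit was late, and they would leave a Week 12 PP analysis under a sensible rule too.

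**4. Exposure.** Twelve weeks of once-daily dosing is 12 × 7 = 84 doses. The PP definition asks for at least one, or 1/84 = 1.2%. Protocol 8.7.1 keeps patients who stop drug early under follow-up for endpoint data, so such a patient could have a Week 12 value. No listed item names missed doses, early stopping or percentage compliance.

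**The case against.** **Follow-up is not irrelevant to this SAP.** Gastrin and CgA are sampled at follow-up (protocol 8.1 and 8.5), and SAP 15 summarises them at every planned visit. A reader might infer that no follow-up window can be defended. The documents do not support that: the window bears on the follow-up gastrin and CgA values. It does not justify removing the same patient's Week 6 and Week 12 values.

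**The primary analysis is not affected.** A reader might infer that the trial's main comparison loses power. It does not under this SAP: the primary endpoint is assigned to ITT, Ki67 is reported elsewhere, no formal test is planned, and the ITT summaries are produced in any case. The power figures apply only to a separate Ki67 per-protocol comparison built on this set. This objection stands and limits the point.

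**The SAP does not commit to keeping under-dosed patients.** A reader might infer that PP is designed to retain patients who barely took drug. SAP 13.2 says "Major protocol deviations include patients who", so the list is open. It names incorrect dose, and it calls for a review of listings before the database closes to "determine whether the data should be excluded from any analysis populations". Missed doses are recorded, compliance is listed, and the study-wide blind is broken only after lock (protocol 7.7). That review could remove such patients before treatment is known. What remains is that it has no stated threshold. The open list does not rescue the window item either: it allows additions but does not cancel what is listed.

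**Conclusion.** The concern holds in a limited form, and its severity is minor. On the current text a late follow-up visit removes a patient, with valid Week 6 and Week 12 data, from PP. In this SAP the consequence is confined to descriptive PP summaries of gastrin and CgA.

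The size rests on assumed, independent lateness rates. Across 5% to 20% per visit, PP loses about 14% to 49% of patients, with 0.9 to 2.6 of 20 lost through follow-up alone. If a Ki67 per-protocol comparison reuses the set, power at 10% lateness is about 77% rather than about 87%, for a difference of 0.25 and SD 0.16. If visits run to time, or lateness clusters in the same patients, the loss is smaller.

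The dosing half is a missing pre-specified threshold and not a rule that retains under-dosed patients.

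**What to change.** In SAP 13.2, replace the blanket window item with a rule by visit:

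- An out-of-window visit loses only its own value from that visit's PP summary.
- A patient leaves a PP change-from-baseline analysis only if a visit supplying that analysis is out of window. For Ki67 these are Visit 2 and Week 12.
- A late follow-up visit then affects only the follow-up gastrin and CgA summary.

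State also whether the separate Ki67 report will use this PP set.

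Secondary: before unblinding, state whether the incorrect-dose item covers low capsule-count compliance or stopping study drug before Week 12, with a threshold that the sponsor sets and justifies.

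The cost is SAP wording, using data already collected. The small downside is that the compliance threshold is a judgement, so it should be fixed while the review is still blinded.

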### **13.3 Baseline Characteristics and Concomitant Medication**

Demographic and baseline characteristics (e.g. , vital signs and ECGs) will be listed and summarised.

Patients who take concomitant medication will be listed and summarised.

Proton Pump Inhibitor use data will be listed.

Medical history including history of Barrett's Esophagus data will be listed and summarised

### **13.4 Treatment Compliance**

The percentage treatment compliance at each visit will be listed and summarised.

## **14 Safety Analyses**

Summaries and listings of safety data will use the safety population.

### **14.1 Extent of Exposure**

The dates and times of first and last treatment dosing will be listed to indicate exposure to the study medication.

### **14.2 Adverse Events**

Adverse events will be coded using the version of the Medical Dictionary for Regulatory Activities (MedDRA) which is current at the time of database lock (version 20.1 or higher).

All adverse events will be listed.

The number of patients with at least one treatment-emergent adverse event (TEAE) will be tabulated by actual treatment and MedDRA system organ class. A treatment-emergent adverse event is defined as an event emerging during treatment having been absent pre-treatment or having worsened relative to pre-treatment.

For each of the following, the number of adverse events and number of patients with adverse events will be summarised by treatment:

- TEAEs by system organ class and preferred term
- Drug-related (“possibly”, “probably” or “definitely” as recorded by the Investigator)  
TEAEs by system organ class and preferred term

Patients with more than one TEAE will be counted only once, at the greatest severity or causality, for each system organ class/preferred term. Multiple TEAEs in a patient will be

counted once per system organ class and preferred term. Adverse events with missing severity and/or causality will be treated as severe and definitely related, respectively.

Summaries will be sorted by system organ class and decreasing total incidence of preferred term.

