11.1 Adverse events (AEs)

- **Reportable adverse events**

All adverse events that occur after the informed consent is signed will be recorded on the adverse event CRF whether or not related to study medication.

- **AE data elements**

- AE reported date
- AE Verbatim Term
- SOC (System Organ Class from MedDRA)
- Common Terminology for Adverse Events v4.0 (CTCAE) AE term
- Event onset date and event ended date
- Severity grade
- Attribution to study medication (relatedness)
- Whether or not the event was reported as a Serious Adverse Event (SAE)
- Whether or not the patient dropped due to the event
- Action taken with the study medication
- Outcome of the event
- Comments

- **Severity of AEs**

Adverse events will be identified using the NCI Common Terminology Criteria for Adverse Events (CTCAE) version 4.0. The CTCAE provides descriptive terminology and a grading scale for each adverse event listed. A copy of the CTCAE can be found

at http://ctep.cancer.gov/protocolDevelopment/electronic_applications/ctc.htm#ctc_40

AEs will be assessed according to the CTCAE grade associated with the AE term. AEs that do not have a corresponding CTCAE term will be assessed according to the general guidelines for grading used in the CTCAE v4.0, as stated below.

- **CTCAE v4.0 general severity guidelines**

(from http://evs.nci.nih.gov/ftp1/CTCAE/CTCAE_4.02_2009-09-15_QuickReference_8.5x11.pdf)

Grade	Severity	Description
1	Mild	Mild; asymptomatic or mild symptoms; clinical or diagnostic observations only; intervention not indicated.
2	Moderate	Moderate; minimal, local or noninvasive intervention indicated; limiting age-appropriate instrumental ADL*.
3	Severe	Severe or medically significant but not immediately life-threatening; hospitalization or prolongation of hospitalization indicated; disabling; limiting self-care ADL**.
4	Life-threatening	Life-threatening consequences; urgent intervention indicated.
5	Fatal	Death related to AE.

- **Activities of Daily Living (ADL)**

*Instrumental ADL refer to preparing meals, shopping for groceries or clothes, using the telephone, managing money, etc.

**Self care ADL refer to bathing, dressing and undressing, feeding self, using the toilet, taking medications, and not bedridden.

- **Assessment of relationship of AE to treatment**

The possibility that the adverse event is related to study medication will be classified as one of the following: not related, unlikely, possible, probable, definite.

- **Follow-up of AEs**

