13.6.1 Adverse Event Analyses

Adverse events (AEs) will be coded using the version of the Medical Dictionary for Regulatory Activities (MedDRA) that is current when the database is locked. All AEs including serious AEs will be mapped to system organ class and preferred term, and will be listed in the data listing.

A treatment-emergent adverse event (TEAE) is defined as an AE that emerges during treatment, having been absent pre-treatment, or that worsens relative to the pre-treatment state.

The number and percentage of patients reporting TEAEs will be tabulated for the safety analysis set by MedDRA preferred term and system organ class, and further by relationship to study drug administered and by severity.

Listings of deaths, SAEs, and AEs that lead to discontinuation of a patient will be presented.

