### **3 Introduction**

This Statistical Analysis Plan (SAP) is based on the current trial protocol (version 24, 26 April 2018). Where statistical methods differ substantially between this SAP and the protocol, that will be identified in this document.

This SAP describes the datasets and the statistical methods to be used for the reporting and analysis of all data collected during the trial except the efficacy data which will be reported separately. Serum gastrin and plasma CgA data will be included in this SAP.

The randomisation code will not be broken before this SAP is finalised. If a future protocol amendment necessitates a substantial change to the statistical analysis of the trial data, this SAP will be amended accordingly. If, after database lock, additional analyses are required to supplement the planned analyses described in this SAP, those unplanned analyses will not be described in an amended SAP, but they will be identified in the integrated clinical study report (CSR). Any deviations from this SAP will be documented in the CSR.

This SAP has been written in consideration of the following guidelines:

- International Conference on Harmonization (ICH) E9, Guidance for Industry: Statistical Principles for Clinical Trials (ICH E9 1998); and
- ICH E3, Guidance for Industry: Structure and Content of Clinical Study Reports (ICH E3 1995).

Statistical analysis will be done using SAS® 9.3 on a Windows PC.

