### 4.2.2 Secondary Endpoints

- Biomarkers
  - Change from baseline at Week 12 in biomarkers potentially associated with esophageal adenocarcinoma, in particular:
    - Change in CCK2R mRNA levels (measured by qRT-PCR)
    - Change in DCAMKL1 expression (measured by IHC)
    - Change in DCAMKL1 mRNA levels (qRT-PCR)
    - Change in COX-2 mRNA levels (qRT-PCR)
    - Change in p53 expression (IHC)
  - Gene expression will be measured using RNA-Seq. Further examination of any changes in expression from baseline may be done using qRT-PCR and IHC
  - Reduction in PPI-induced increase in plasma CgA
  - Increase in PPI-induced hypergastrinaemia
- Safety
  - Vital signs, ECG, physical examination, laboratory safety tests: blood tests: red blood cells (RBC), haemoglobin, haematocrit, platelets, white blood cells (WBC, differential: neutrophils, bands, lymphocytes, monocytes, eosinophils, basophils), sodium, potassium, magnesium, chloride, bicarbonate, creatinine, serum glucose, blood urea nitrogen (BUN), alkaline phosphatase, lactate dehydrogenase (LDH), serum glutamic-oxaloacetic transaminase/aspartate amino transferase (SGOT/AST), serum glutamicpyruvic transaminase/ alanine aminotransferase (SGPT/ALT), total bilirubin, total protein, albumin, calcium, amylase, lipase; and urine tests: pH, specific gravity, protein, glucose, ketones, blood.
  - Change in histology
- Tolerability: assessment of adverse events.
- Pharmacokinetics: trough and peak concentration of netazepide

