## 17 Changes from the Protocol Specified Statistical Analysis

After the study was submitted to the regulatory authorities and ethics committee the following changes were made to the analyses:

- Section 13.1 Analysis Sets of the protocol states “The pharmacokinetic analysis set will include all patients who receive at least one dose of study medication, and yield at least one plasma concentration for netazepide.” This definition is not included in the SAP as the population is not required.

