## **19 ATTACHMENTS**

### **19.1 Table of Contents for Data Display Specifications**

For overall page layout refer to Appendix B.

The numbering in the tables below will take precedence over the numbering in the shells.

The following tables and figures will be produced (templates provided in Section 19.2.1 and 19.2.2):

Table	Description	Population	Source Listing	Template (Shells below)
10.1	Summary of patient disposition	Safety	16.2.1.2 16.2.3.1	T_SD1
10.2.1	Summary of concomitant medications	Safety	16.2.4.2	T_CM1
10.2.2	Summary of medical history: barrett's esophagus	Safety	16.2.4.3	T_MH1
10.2.3	Summary of treatment compliance	Safety	16.2.5.1	T_COMP1
14.1	DEMOGRAPHIC DATA			
14.1	Summary of demographic characteristics	Safety	16.2.4	T_DM1
14.2	PHARMACOKINETIC and EFFICACY			
14.2.1	Summary of netazepide plasma peak and trough concentration data	Safety	16.2.6.1	T_PK1
14.2.2.1	Summary of serum gastrin and plasma CgA data (ITT)	ITT	16.2.6.2	T_EG2
14.2.2.2*	Summary of serum gastrin and plasma CgA data (PP)	PP	16.2.6.2	T_EG2
14.3	SAFETY DATA			
14.3.1.1	Summary of treatment-emergent adverse events	Safety	16.2.7.1	T_AE1
14.3.1.2	Summary of drug-related treatment-emergent adverse events	Safety	16.2.7.1	T_AE1
14.3.2.1	Listing of fatal adverse events	Safety	16.2.7.1	L_AE1_PG
14.3.2.2	Listing of non-fatal serious adverse events	Safety	16.2.7.1	L_AE1_PG
14.3.2.3	Listing of other significant adverse events	Safety	16.2.7.1	L_AE1_PG
14.3.3	Narratives of deaths, other serious and significant adverse events	Safety	-	-
14.3.4	Summary of laboratory values of potential clinical importance	Safety	16.2.8.1, 16.2.8.3	T_LB1
14.3.5.1	Summary of chemistry laboratory values	Safety	16.4	T_LB2
14.3.5.2	Summary of haematology laboratory values	Safety	16.4	T_LB2
14.3.5.3	Summary of urinalysis results	Safety	16.4	T_UR1
14.3.6.1	Summary of vital signs	Safety	16.4	T_VS1
14.3.7.1	Summary of ECG values	Safety	16.4	T_EG2
14.3.7.2	Summary of ECG values and changes in ECG values of potential clinical importance	Safety	16.4	T_EG3

Figure	Description	Population	Source Listing	Template (Shells below)
14.3	SAFETY AND EFFICACY DATA			

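### The SAP omits the by-severity adverse event table that protocol 13.6.1 requires without declaring it, and plans no summary of the histology safety endpoint

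*SAP*

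**What the plan says.** **Severity.** Protocol 13.6.1 asks for numbers and percentages of patients with TEAEs by preferred term and system organ class, "and further by relationship to study drug administered and by severity". The data will exist, because protocol 11.1 states that "AEs will be assessed according to the CTCAE grade associated with the AE term", on a scale of 1 to 5.

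SAP 14.2 gives this counting rule: "Patients with more than one TEAE will be counted only once, at the greatest severity or causality, for each system organ class/preferred term". It also says that an event with missing severity is treated as severe, and one with missing causality as definitely related. The index in SAP 19.1 has two TEAE summaries: table 14.3.1.1, "Summary of treatment-emergent adverse events", and table 14.3.1.2, "Summary of drug-related treatment-emergent adverse events". Both use shell T_AE1.

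**Histology.** "Change in histology" is listed under Safety in SAP 4.2.2, as it is in protocol 1.9 and 9.2. SAP 3 sets the scope of the SAP as "all data collected during the trial except the efficacy data which will be reported separately", and then brings serum gastrin and CgA back in.

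**Declared changes.** SAP 17 begins by saying that "the following changes were made to the analyses" and lists one item, the dropped pharmacokinetic analysis set. Protocol 13.2 undertakes that the SAP will describe in full any departure from the protocol's planned analyses.

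**The concern.** One stated aim is to learn whether the drug is safe in patients with Barrett's esophagus. Two by-arm summaries that bear on that aim are missing from the planned outputs.

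The first is an analysis that the protocol explicitly promised. Without it, the summary tables show how many patients per arm had an event, or a drug-related event, but not how bad the events were.

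The second is an endpoint that both documents name and neither says how to analyse. The trial enrols patients without dysplasia and repeats the biopsies at Week 12. A change in histology on treatment is therefore a safety question specific to this population. As the SAP stands, the endpoint has no assigned place in this report or in any other.

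**Working it through.** No power or sample-size calculation applies. The check compares what the protocol asks for with what the SAP will produce.

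**Severity**

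| Item | Where | Content |
|---|---|---|
| Requirement | Protocol 13.6.1 | TEAEs by class and term, by relationship, and by severity |
| Data collected | Protocol 11.1 | CTCAE v4.0 grade for each event |
| Summaries in text | SAP 14.2 | All TEAEs; drug-related TEAEs |
| Tables in index | SAP 19.1 | 14.3.1.1 and 14.3.1.2 |
| Shell for both | SAP 19.2.1, T_AE1 | Class, term, patients n (%), number of events; no severity row or column |
| Listing | SAP 19.1 (16.2.7.1), shell L_AE1_PG | Severity shown for each event |
| Declaration | SAP 17 | Pharmacokinetic set only |

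TEAE summary tables planned: 2. By severity: 0. Items in section 17: 1. About severity: 0.

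The rules in SAP 14.2 suggest an oversight more than a decision. Their causality half is used, since table 14.3.1.2 must classify events as related or not. Their severity half has no table to work on. The missing-severity rule is also worded as severe, while the protocol grades from 1 to 5. The protocol's general guidelines give that label to grade 3, but the SAP does not state the grade.

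To show what a table without severity can hide, assume 10 patients per arm (protocol 13.7) and invented counts:

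- Any TEAE: 6/10 = 60% in each arm, so the overall row of table 14.3.1.1 is the same for both.
- Grade 2 or higher: 5/10 = 50% in one arm and 0/10 = 0% in the other.

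The overall row would not show that difference. Listing 16.2.7.1 would, event by event.

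**Histology**

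1. Both documents class it as safety. The list of efficacy variables in protocol 13.4 does not contain it.
2. The scope exclusion in SAP 3 covers efficacy data only, so histology stays within this SAP.
3. SAP 14.1 to 14.6.2 cover exposure, adverse events, laboratory tests, vital signs and ECG. SAP 19.1 and 19.2 have no table, figure or named listing for on-study histology. The Barrett's history listing (shell L_MH1) records findings from before the trial. Planned named outputs: 0.
4. The protocol is little better. Sections 13.6.1 to 13.6.3 cover adverse events, laboratory tests and ECG. Only the general sentence in 13.6, that safety data will be summarised and listed, reaches histology.

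The form of a usable summary follows from protocol 8.7.2. Patients are withdrawn if the Visit 2 biopsies show no intestinal metaplasia, or are read as indefinite, low-grade dysplasia, high-grade dysplasia or adenocarcinoma. Of six possible baseline categories (those five and non-dysplastic Barrett's), only one should have Week 12 data. A shift table therefore reduces to one row: Week 12 category among patients who were non-dysplastic at Visit 2. Under protocol 8.2, drug is dispensed at Visit 2 and started the next day. Patients withdrawn on their Visit 2 reading may thus have taken study drug, and they need a separate count.

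**The case against.** The strongest reply is that little is lost. Listing 16.2.7.1 covers all adverse events and its shell includes severity, seriousness and withdrawal. SAP 11.1 sorts listings by treatment group. There are separate listings for fatal, serious and other significant events and for events leading to withdrawal. With about 20 patients, anyone could count grades by arm, and the SAP plans no formal testing. This is fair and limits the harm, so a reader who inferred that severity would be invisible would be wrong. It does not supply the tabulation that the protocol specified, and it does not explain the silence in section 17.

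Four other stronger readings are not supported:

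- A reader might take grade 2 as a stopping threshold that the outputs fail to report. Protocol 8.7 only permits the patient or investigator to stop at grade 2 or above, as one of several reasons.
- A reader might conclude that the SAP's severity and causality rules feed no output. The causality half feeds table 14.3.1.2, and counting each patient once is the footnote to T_AE1.
- A reader might charge section 17 with hiding a change to the histology analysis. The protocol specifies no particular histology analysis, so there is no clear change to declare. This is a gap common to both documents.
- A reader might want a full shift table from Visit 2 to Week 12. The withdrawal rule in 8.7.2 leaves most of it empty.

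The sponsor could also say that histology will come with the separately reported biopsy results. That is possible, since the readings are made in a pathology department and UK slides may be sent only at the end of the study (protocol 10.3.2). But both documents class the endpoint as safety, so the SAP needs to say so. Protocol 4.2 also calls the diagnosis of low-grade dysplasia very poorly reproducible, so small differences in that category would be hard to interpret.

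**Conclusion.** The point stands as two separate faults of unequal weight.

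The severity fault is a direct and undeclared departure. The protocol requires a by-severity tabulation, neither of the two planned TEAE tables provides it, and section 17 is silent. The information survives only at listing level.

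The histology fault is a named safety endpoint without an analysis in either document and without a summary or named listing in the SAP. It is a lack of specification, not a concealed change.

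Both are reporting corrections that should be made before unblinding. Neither affects the primary endpoint or the power. The conclusion assumes that the SAP's index and shells are the full set of planned summaries. SAP 19.1 adds that complete data listings will also be produced, but these are not by-arm summaries.

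**What to change.** 1. Add a by-arm TEAE table by system organ class and preferred term at maximum CTCAE grade, using the greatest-severity rule already in SAP 14.2. State the missing-severity rule as a CTCAE grade. If the table is not wanted, declare and justify its omission in section 17.
2. Add a by-arm count of Week 12 histology category among patients whose Visit 2 biopsies showed non-dysplastic Barrett's esophagus. Count patients withdrawn because of their Visit 2 histology separately. Keep the summary descriptive. Alternatively, state in the SAP which report will carry this endpoint.

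The cost is two small table shells and their programming. Grade is already collected, and biopsies from both endoscopies are reviewed for dysplasia. The documents do not show that on-study histology is held in the analysis database. If it is not, the pathology readings must also be transferred. With about 10 patients per arm many cells will be small, so the tables will describe the data and will not support inference.
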